Early clinical experience with favipiravir for COVID-19 is promising. An open-label nonrandomized trial of 80 patients with COVID-19 in China identified a significant reduction in the time to SARS-CoV-2 viral clearance in patients treated with favipiravir compared to historical controls treated with lopinavir/ritonavir. Patients with mild or moderate COVID-19 were enrolled within 7 days from disease onset; those with severe or critical disease, ≥ 75 years old, chronic liver disease, or end-stage renal disease were excluded. Patients in the intervention arm received Favipiravir 1600 mg PO BID on day 1 followed by 600 mg PO BID on days 2-14. Both arms were co-treated with inhaled IFN- $\alpha 1b$ 60 μg BID and therapy was continued until viral clearance, up to a maximum of 14 days. Thirty-five patients were assigned to favipiravir and 45 patients to lopinavir/ritonavir, with a median age of 47 (IQR 35.8-61); 13.7% were ≥ 65 years old. There was a significant reduction in the median time to viral clearance with favipiravir (4 days; IQR 2.5-9) as compared to lopinavir/ritonavir (11 days; IQR 8-13; p <0.001). Further, by day 14, 91.4% of patients in the favipiravir arm had radiographic improvement versus 62.2% of the lopinavir/ritonavir arm. There was a significantly lower rate of adverse events in patients receiving favipiravir (11.4% v. 55.6%, p<0.01).

In an open-label randomized trial in China, 240 patients with confirmed COVID-19 were randomized to favipiravir or arbidol. Favipiravir was given at 1600 mg PO twice on day 1 followed by 600 mg PO BID until day 7-10. The clinical recovery rate by day 7 of treatment was higher amongst patients receiving favipiravir, albeit not achieving statistical significance (61.21% v. 51.67%, p=0.1396). Amongst patients with moderately severe disease, there was a significantly higher rate of clinical recovery by day 7 with favipiravir (71.43% v. 55.86%).

Given the demonstrated in-vitro of activity of favipiravir against SARS-CoV-2 and signals of benefit in early clinical experience for COVID-19, further studies are urgently needed. To address this need, there are several active clinical trials to assess the therapeutic efficacy for COVID-19. However, no trials to date have focused on outbreak control, an area of significant need. It is critical to evaluate the efficacy of favipiravir as chemoprophylaxis against COVID-19 using a placebo-controlled randomized trial.

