Symptomatic microbiologically confirmed COVID-19 disease in residents: a respiratory specimen (e.g. nasopharyngeal swab) yielding SARS-CoV-2 RNA in association with new onset fever (≥37.8°C) OR cough OR one or more of the following other respiratory or systemic symptoms (fatigue, myalgias, arthralgias, shortness of breath, sore throat, chills, loss of appetite, vomiting or diarrhea, change in level of responsiveness or capacity for activities of daily living (ADL)), OR requirement for hospitalization OR death.

Symptomatic microbiologically confirmed COVID-19 disease in staff: fever (≥38.0°C or cough or two or more of the following other respiratory or systemic symptoms (fatigue, myalgias, arthralgias, shortness of breath, sore throat, chills, loss of appetite, anosmia, vomiting or diarrhea).

Unit

A unit is the section of the LTCH experiencing an outbreak which will be randomized to study drug. Units are sections within the LTCH which have a nursing station and shower room and on which residents and most staff can be reliably physically separated from residents of other units for the duration of the outbreak. Units with >32 residents will be excluded.

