6. STUDY OBJECTIVES AND DESIGN

6.1 Overall Study Design (figure 1)

This study is a partially blinded, placebo-controlled cluster randomized trial of chemoprophylaxis to control outbreaks of COVID-19 in LCTHs for the elderly. The unit of analysis is a ward/unit. This design is selected to mimic the current approach to outbreaks of other respiratory viral infections, both because this approach has proven effective for these other viruses, and because it is standard practice and therefore feasible to implement.

Eligible LTCHs will be asked to report outbreaks to the study in addition to the legally-required reporting to their local public health unit; public health units will also be asked to discuss the study with LTCHs reporting outbreaks. In addition, study staff will contact the infection control practitioner in each of the screened LTCHs twice weekly, to ensure the prompt identification of outbreak units.

Either pre-study, or at baseline (identification of the outbreak), residents and staff will be assessed for contraindications to enrollment and informed consent will be obtained for residents and staff to receive the allocated intervention, and to be followed up individually for clinical outcomes, adherence and safety during the outbreak. Favipiravir or placebo will be offered to all residents and staff who will be working on the unit during the chemoprophylaxis period, according to the allocation. Surveillance for infection will occur as usual for resident illness within each facility; staff will be asked to report symptoms and will be screened for symptoms each time they enter the building. Consenting residents and staff will be screened at day 0, day 14 and day 40 to identify asymptomatic infections and to assess duration of viral shedding. The primary outcome will be control of the outbreak, defined as no new microbiologically confirmed case of COVID-19 for 24 consecutive days up to day 40.

STUDY SCHEME

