6.4 Endpoint Assessment

The primary outcome (primary endpoint) will be control of outbreak, defined as no new cases of COVID-19 in residents for 24 consecutive days up to day 40 after the start of prophylaxis. This outcome is dichotomous (yes/no) and will be determined at the level of the cluster (LTCH unit).

Secondary outcome measures (endpoints) are:

- 1. The proportion of residents of included LTCH units who die up to day 40, and up to day 60
- 2. The proportion of residents of included LTCH units who were uninfected at baseline and develop new symptomatic microbiologically confirmed COVID-19 up to day 40
- 3. The proportion of exposed staff uninfected at baseline in whom SARS-CoV-2 infection is identified up to day 14 and up to day 40
- 4. The proportion of residents of included LTCH units hospitalized up to day 40
- 5. The proportion of residents of included LTCH units who discontinue study medication due to adverse events
- 6. The proportion of LTCH staff of included LTCH units who discontinue study medication due to adverse events.
- 7. The occurrence of new microbiologically confirmed COVID-19 infections in residents in other units of the facility up to day 40 (dichotomous, at LTCH level)
- 8. The proportion of previously unaffected LTCH units of the remainder of the facility in which a case of COVID-19 is identified
- 9. The proportion of residents in the remainder of the facility who develop COVID-19 infections up to day 40

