12.2 Laboratory Evaluations and Specimen Collection

12.2.1 Microbiologic testing for SARS-CoV-2

It is expected that all residents or staff who meet the case definition for COVID-19 will have specimens obtained clinically for testing, the results from which will be recorded. However, if any such cases do not meet criteria for clinical testing, specimens will be submitted to the study laboratory for testing in real time. Any resident who dies in the home during the study period will have a nasopharyngeal swab submitted for COVID-19 testing.

At baseline (day 0) and on day 14 and day 40, participants will undergo collection of nasopharyngeal or nasal swab for RT-PCR testing. Testing will be performed using licensed tests for COVID-19 by research laboratories licensed to perform such tests.

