13.3 Baseline Visit (Day 1)

• Dispense study drug:

- Medications are provided to LTCH residents in Ontario by third-party pharmacies. The pharmacies for participating LTC facilities will be approached in advance to coordinate mechanisms for timely distribution of trial drugs. Medications will be distributed from the central research pharmacy to the regional dispensing pharmacy for distribution to the LTCH. All medications will be dispensed and administered by long-term care facility nursing staff as part of routine medication administration.
- o For staff, the medication will be dispensed from the research pharmacy to study research coordinators who will be responsible for arranging transportation to the study participants and documenting this process.

13.4 Data collection Day 2 to Day 40

Efforts will continue to ensure that either an electronic or hard copy of the signed written informed consent form is obtained from each participant or their substitute decision maker. This should be obtained as soon as possible, ideally by day 2.

From day 0 until the outbreak is declared over, the LTCH will fax daily line lists of the outbreak to the study (these will already be being routinely sent to the local public health unit). These lists record all residents and staff who meet the case definition, who are tested for COVID-19, as well as the results of any testing. For this study, we will add to the line list a record of any potential adverse events, and discontinuation of study drug. Study staff will also report any deaths or transfers to hospitals during the outbreak. In addition, the study coordinator responsible for the particular outbreak will participate in all virtual outbreak meetings between public health units and the LTCH, to ensure that no information is missed.

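### Secondary outcome 3: staff infections found only by the day 14 and day 40 swabs may be detected differently by arm, so a lower count does not by itself show prevention

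*Protocol*

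**What the plan says.** Protocol 6.3 and 6.4 define secondary outcome 3 as "The proportion of exposed staff uninfected at baseline in whom SARS-CoV-2 infection is identified up to day 14 and up to day 40". It is not limited to symptomatic disease, whereas the resident counterpart (outcome 2) is.

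Infection in staff can be identified by two routes.

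- **Testing prompted by symptoms, at any time.** Section 6.1: "staff will be asked to report symptoms and will be screened for symptoms each time they enter the building". Section 12.2.1 expects that "all residents or staff who meet the case definition for COVID-19 will have specimens obtained clinically for testing", with the study laboratory as back-up. Under Section 13.4 the daily "lists record all residents and staff who meet the case definition, who are tested for COVID-19, as well as the results of any testing".
- **Scheduled swabs.** Section 12.2.1: "At baseline (day 0) and on day 14 and day 40, participants will undergo collection of nasopharyngeal or nasal swab for RT-PCR testing". Section 6.1 gives their purpose: participants are "screened at day 0, day 14 and day 40 to identify asymptomatic infections and to assess duration of viral shedding".

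Section 5 defines "Symptomatic microbiologically confirmed COVID-19 disease in staff" by fever, or cough, or at least two other listed symptoms. No listed endpoint uses this definition. No serology and no swab between days 14 and 40 is described for staff without qualifying symptoms. Under Section 10.1 staff take study drug until day 25.

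On viral clearance, Section 4.2 reports from one study: "There was a significant reduction in the median time to viral clearance with favipiravir (4 days; IQR 2.5-9"), against 11 days (IQR 8-13) on lopinavir/ritonavir. Section 5, in the rationale for outbreak control, says it is not yet known whether any drug works as therapy or pre-emptive therapy.

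**The concern.** For an infection that never meets the staff case definition, a swab shows whether RNA is present that day, not whether infection occurred since the last swab. An infection that began and cleared between swabs is counted as no infection. That loss is harmless to the comparison if it is equal in both arms. It is not equal if the drug changes how long RNA stays detectable. At day 14 every staff member still taking the assigned treatment is on study drug, so the detection window itself may depend on the arm. Randomisation and blinding do not remove this, because it follows from treatment.

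At stake is how a lower staff count on favipiravir is read. It could be reported as a prophylactic effect when faster clearance in the same number of infected staff would produce the same pattern. The analysis cannot recover infections that were never detected.

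**Working it through.** The protocol gives no figure for outcome 3, so there is none to reproduce. The only design figure is the primary-outcome power of more than 85%. Exact enumeration of Fisher's test with 8 against 8 units at 12.5% and 87.5% gives 0.870, and this point does not affect it.

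**Inputs from the protocol:** swabs on days 14 and 40; study drug to day 25; clearance quartiles 2.5, 4, 9 days (favipiravir) and 8, 11, 13 days (comparator).

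**Assumptions, not in the protocol:**

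- no preventive effect;
- infections uniform over days 0-14;
- positivity starting 2 or 4 days after infection;
- the cited clearance times stand for the duration of PCR positivity, with the comparator standing for placebo;
- all symptomatic infections are caught;
- a share a = 20, 40 or 60% of infections is asymptomatic.

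**Step 1: shedding distribution.** A lognormal with one spread per arm, ln(Q3/Q1)/1.349, does not reproduce the cited upper quartiles. It gives 11 × exp(0.6745 × 0.360) = 14.0 days instead of 13, and 4 × exp(0.6745 × 0.950) = 7.6 days instead of 9. I therefore used a separate spread below and above the median, ln(median/Q1)/0.6745 and ln(Q3/median)/0.6745, which matches all three quartiles.

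**Step 2: asymptomatic infections positive on day 14** (simulation):

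| Lag to positivity | Placebo (p) | Favipiravir (f) | f/p |
|---|---|---|---|
| 2 days | 0.704 | 0.404 | 0.57 |
| 4 days | 0.635 | 0.375 | 0.59 |

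**Step 3: apparent rate ratio for the whole outcome at day 14**, RR = [(1 − a) + a·f] / [(1 − a) + a·p]:

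| a | Lag 2 days | Lag 4 days | About |
|---|---|---|---|
| 20% | 0.881/0.941 = 0.94 | 0.875/0.927 = 0.94 | 0.94 |
| 40% | 0.762/0.882 = 0.86 | 0.750/0.854 = 0.88 | 0.87 |
| 60% | 0.642/0.822 = 0.78 | 0.625/0.781 = 0.80 | 0.79 |

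**Step 4: smaller shedding difference.** With medians of 11 and 9 days and the same relative spread, the ratios are about 0.98, 0.97 and 0.95.

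**Step 5: cross-check with a simpler model.** Take fixed positivity of 11 and 4 days, with onset of positivity uniform over the period.

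- To day 14, swabs alone find 11/14 = 79% against 4/14 = 29%, a ratio of 0.36. If symptom testing catches 50% or 80% of infections, the ratio is 0.72 or 0.90.
- To day 40, with positivity back to 11 days for onset after day 25, placebo gives 11/40 + 11/40 = 55% and favipiravir 4/40 + 11/40 = 37.5%, a ratio of 0.68. With 50% or 80% caught by symptoms it is 0.89 or 0.96.

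In this model the day 40 swab finds 11/40 in both arms, so the whole cumulative difference comes from the day 14 swab.

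**The case against.** The strongest reply has five parts.

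1. **The endpoint is not swab-only.** Staff are screened at each entry, the case definition is broad, and results reach the study through line lists. This stands. It confines the problem to infections that do not meet the case definition, and the ratios above already assume full capture of the rest.
2. **The protocol does not predict shorter shedding.** A reader might infer from Section 4.2 that it expects this, so that faster clearance will look like prevention. The documents do not support that. The 4 against 11 days comes from a non-randomised study of diagnosed patients against another antiviral, both groups also given interferon, and Section 5 calls efficacy unknown. The right word is can. The transfer of those times to asymptomatic staff on prophylaxis is my assumption.
3. **Viral suppression is partly intended.** Section 5 counts pre-emptive therapy of people with detectable virus as chemoprophylaxis. This is fair, but the outcome is worded as infection in staff uninfected at baseline, and a lower count would be read as prevention.
4. **Symptomatic disease is already analysed.** Section 15.3.2 plans time-to-event models for its onset, not limited to residents, and separate reporting could sit in a statistical analysis plan that is not shown. This reduces the weight of the point. Still, no listed endpoint uses the staff definition, and the limit on interpretation belongs with the endpoint.
5. **Restricting outcome 3 to symptomatic disease is no cure.** A reader might infer that it should be replaced. That would abandon the stated aim of finding asymptomatic infection, and a drug that only softened symptoms would then look preventive. This stands, and replacement is not recommended.

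A reader might also take the two swab dates as a fault in measuring shedding duration. Section 6.1 names that as a purpose, but no listed endpoint depends on it. Nor do the cited quartiles support a large contrast in long shedding: the matched fit puts about 17% against 15% beyond 14 days.

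**Conclusion.** The point holds for the swab-only part of secondary outcome 3. That part is open to differential detection by arm, and a lower count there cannot separate prevention from faster clearance. The exposure is mainly at day 14. By the day 40 swab, staff have been off drug for 15 days, and infections acquired after day 25 are not distorted by treatment.

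Under no prevention, the false rate ratio at day 14 is about 0.94, 0.87 or 0.79 for 20, 40 or 60% asymptomatic infections. It moves towards 1 as the shedding difference shrinks or as symptom testing captures more infections. The asymptomatic share and the true shedding difference are not in the documents, so these figures show a possible size, not a forecast. The point concerns one of nine secondary outcomes; the primary outcome is measured in residents and is unaffected. It is a modest improvement worth making because it is cheap.

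**What to change.** Keep outcome 3 as defined. In 6.3 and 6.4, require that it also be reported by arm as two components:

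- (a) symptomatic microbiologically confirmed COVID-19 in staff, using the Section 5 definition and dated by onset, up to day 14 and up to day 40;
- (b) positives found only by the scheduled swabs, given as point prevalence of RNA positivity at day 14 and at day 40.

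Add one sentence stating that a difference confined to (b) will not be interpreted as prevention of infection.

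The cost is a wording change and a little more analysis. Diaries, clinical test results, line lists and scheduled swabs are already collected. The drawback is few events in each component, so each will be estimated imprecisely.

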9. ALLOCATION AND BLINDING PROCEDURES

9.1 Allocation

Each nursing home unit will only be randomized once all members of the unit or their substitute decision makers (SDMs) give preliminary consent, decline or are classified as not contactable; at least 80% of residents or their SDMs within the unit must give consent to take the study medication (favipiravir or placebo) for unit eligibility for randomization. Every effort will be made to contact residents and/or their substitute decision makers within 48 hours. Those who cannot be contacted within 96 hours will not be eligible to receive study drug. LTCH staff may be enrolled on a continuing basis, recognizing that new LTCH staff may be needed to start work on the unit during the outbreak.

As LTCH units will be enrolled prospectively, we will use probabilistic minimization on the baseline COVID-19 attack rate on the unit to allocate units 1:1 (8 intervention units, 8 control units) to the 2 groups. Probabilistic minimization will be performed by an independent statistician at the Applied Health Research Centre (AHRC) at St. Michael's Hospital using the R package *minirand* (R Foundation for Statistical Computing, Vienna, Austria). Consent of LTCH staff and residents prior to randomization of the cluster, and use of placebo as a control intervention will help minimize the risk of "empty" clusters or the use of interventions that are not part of this protocol.

Each person for whom written informed or preliminary verbal consent was obtained will be entered in the electronic case report form (eCRF) so that an adequate number of uniquely coded study drug bottles/blister packes for all consenting members of the LTCH unit can be prepared. An automated audit trail will record the time, date, allocation, and participant identification numbers. Those who withdraw preliminary consent or decline study drug will be asked to consent to be followed-up for primary and secondary outcome. Those who also decline follow-up will be excluded from intention-to-treat analyses. Waiver of consent will be requested of participating sites to record the number of non-participating residents and LTCH staff, and the number and date of onset of cases of symptomatic microbiologically confirmed COVID-19 in these two groups.

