15.3.2 Analysis of Secondary Outcome Measures

Secondary analyses will include generalized linear mixed models (GLMMs) with logit link to estimate the effect of favipiravir on the probability of the secondary outcomes at participant level, while accounting for clustering of participants in LTCHs. We will also compare the onset of symptomatic disease, hospitalization, and mortality in time-to-event models. All analyses will be by intention-to-treat.

Safety outcomes will include the number of serious adverse events in residents and staff, and the proportion of residents and staff whose study medications are discontinued due to adverse events

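### Discontinuation due to adverse events (outcomes 5 and 6) is counted over a denominator that can include followed-up people who never took study drug, which lowers each arm's reported rate

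*Protocol*

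**What the plan says.** Protocol section 6.4 lists two tolerability measures among the secondary outcomes. Outcome 5 is "The proportion of residents of included LTCH units who discontinue study medication due to adverse events" and outcome 6 is "The proportion of LTCH staff of included LTCH units who discontinue study medication due to adverse events". The synopsis and section 6.3 repeat both. Neither carries a condition on having taken the drug, although outcomes 2 and 3 in the same list do restrict their denominators, to people uninfected at baseline.

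Section 15.3.2 states "All analyses will be by intention-to-treat". It then names, among the safety outcomes, "the proportion of residents and staff whose study medications are discontinued due to adverse events". No exception to intention-to-treat is made for safety.

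Section 9.1 determines who is followed:

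- Before a unit is randomized, "at least 80% of residents or their SDMs within the unit must give consent to take the study medication". This floor concerns residents only; staff have none.
- People who refuse the drug, or take back a preliminary consent, are invited to stay in follow-up for the trial's outcomes.
- Of these, only people who refuse follow-up as well leave the analysis set: "Those who also decline follow-up will be excluded from intention-to-treat analyses".

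**The concern.** A person who never took study drug cannot stop it because of an adverse event. Such a person adds one to the denominator and can never add to the numerator. Two groups can enter the analysed set this way: people who decline drug or withdraw preliminary consent but accept follow-up, and consenters who never start.

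For efficacy outcomes, keeping these people in is right. For a discontinuation rate it pulls the figure towards zero, which for a safety measure is the unsafe direction. A reader judging a 25-day course in frail residents, and in staff, will look at the proportion who stopped in each arm and at the absolute difference. Both depend on how many undosed people are in the denominator, and that can vary from unit to unit.

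**Working it through.** **The plan's own figure.** The protocol states no rate, uptake or power for outcomes 5 and 6. Its only power figure, above 85%, concerns the primary outcome; full enumeration of the two-sided Fisher test (8 vs 8 units, 12.5% vs 87.5%) gives 0.870, so it reproduces. It has no bearing on this point.

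**Inputs.**

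- Minimum share of unit residents consenting to drug: 0.80 (section 9.1).
- Discontinuation rates among those dosed: none given. Assumed p1 = 10% on favipiravir and p0 = 5% on placebo, for illustration.
- Share of non-consenters who accept follow-up, f, and share of consenters who start, s: none given; varied below.

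**Step 1, dilution.** If a share c of the denominator took at least one dose, the reported rate is c × p. With equal c in both arms the reported difference is c × (p1 − p0).

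| c | Reported rates | Difference |
|---|---|---|
| 1.00 | 10% vs 5% | 5.0 points |
| 0.90 | 9% vs 4.5% | 4.5 points |
| 0.80 | 8% vs 4% | 4.0 points |
| 0.70 | 7% vs 3.5% | 3.5 points |
| 0.50 | 5% vs 2.5% | 2.5 points |

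**Step 2, what c can be for residents.** With consent at the floor, c = 0.80s / (0.80 + 0.20f).

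- f = 1, s = 1: c = 0.80/1.00 = 0.80, a 20% relative shortfall.
- f = 0.5, s = 1: c = 0.80/0.90 = 0.889, an 11% shortfall.
- f = 0, s = 1: c = 1, no shortfall.
- f = 1, s = 0.95: c = 0.76, a 24% shortfall, because the floor is on consent and not on starting.

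**Step 3, staff.** There is no consent floor and no stated uptake. What matters is the share of followed staff who never took a dose, and the protocol gives nothing from which to estimate it.

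**Step 4, the planned effect measure.** Section 15.3.2 specifies logit-link mixed models for participant-level secondary outcomes, so the comparison is an odds ratio. The figures below are simple, unclustered odds ratios.

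- Among dosed: (0.10/0.90) / (0.05/0.95) = 2.11.
- At c = 0.80: (0.08/0.92) / (0.04/0.96) = 2.09.
- At c = 0.50: (0.05/0.95) / (0.025/0.975) = 2.05.
- With higher assumed rates, 30% vs 10%: 3.86 among dosed, 3.63 at c = 0.80.

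The risk ratio stays at 2.00 for 10% vs 5%. Power ignoring clustering also hardly changes. Assuming 24 residents per unit (8 × 24 = 192 per arm), it is 0.384 with 154 dosed per arm and 0.378 with all 192 at the diluted rates.

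**Step 5, unequal uptake.** With 80% dosed on favipiravir and 100% on placebo, 0.10 × 0.80 − 0.05 × 1.00 = 3 points. Reversed, 0.10 × 1.00 − 0.05 × 0.80 = 6 points. The difference among those dosed is 5 points in both cases.

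**The case against.** The best case on the other side has four parts.

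1. *The denominator is narrower than the endpoint wording.* A reader might infer that everyone living or working on the unit is counted. Section 9.1 does not support that: it drops people who decline both drug and follow-up. For non-participants, the waiver it describes covers only their number and their COVID-19 cases, with no medication or adverse event data. Consent is also an inclusion criterion for residents and staff (sections 7.1.2 and 7.1.3). This stands, and it confines the problem to followed-up people who never took a dose.

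2. *The comparison between arms is barely affected.* A reader might infer that the treatment effect itself is understated. On the planned odds-ratio scale it is not, to any material degree. On the absolute scale it shrinks under equal uptake but can move either way otherwise. This stands too; the firm harm is to each arm's reported rate.

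3. *A safety set may be defined in a statistical analysis plan that is not shown.* That is true, and its absence from the protocol is no fault. But the protocol states a denominator and applies intention-to-treat without exception. A plan that used a dosed-only denominator would contradict that text.

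4. *The intention-to-treat sentence closes the paragraph on secondary-outcome models, and the safety outcomes come in the next paragraph.* This leaves some doubt over the safety restatement. It does not release outcomes 5 and 6, which section 6.4 lists as secondary outcomes.

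**Conclusion.** The point holds in limited form. As worded, outcomes 5 and 6 can count followed-up people who never took study drug, and each arm's discontinuation rate is then too low by the undosed share of the denominator. With equal uptake the absolute difference is too small by the same proportion.

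For residents, 20% relative is a conditional figure: consent exactly at the floor, every non-consenter followed and every consenter starting. Fewer followed non-consenters make it smaller; consenters who never start make it larger. The 10% and 5% rates are assumptions.

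For staff, the missing floor might suggest a very large understatement. The documents do not support any number there, because uptake among all unit staff is not uptake among the staff who are analysed. The size is unknown.

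Nor do the documents show that the comparison must favour the drug. That direction follows for each arm's rate, and for the absolute difference only if uptake is similar in the two arms.

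**What to change.** In the synopsis and sections 6.3, 6.4 and 15.3.2, define outcomes 5 and 6, and the matching safety outcome, among participants who took at least one dose of study drug, grouped by allocated arm. Exempt them from the intention-to-treat sentence in 15.3.2, and keep intention-to-treat for the efficacy outcomes. Reporting the number followed but never dosed in each arm would let readers see whether uptake was balanced.

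The cost is wording only. The data needed are already planned: recorded medication administration and adherence checks for residents, and diaries and a pill count for staff. The downside for the sponsor is that the reported discontinuation rates become slightly less favourable.
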